2.2. Study Design

[figure not shown]
This is a phase 1, open-label, multicenter study to evaluate the safety and tolerability of HMPL 306 administered orally (PO) in treatment of patients with locally advanced or metastatic solid tumors with IDH mutation. The study consists of 2 parts: Part 1 (dose escalation) and Part 2 (dose expansion). Only part 1 included in this analysis plan.

The first part of the study is dose escalation where cohorts of patients will receive ascending oral doses of HMPL-306 to determine maximum tolerated dose (MTD) and/or the recommended phase 2 dose (RP2D). The modified toxicity probability interval-2 (mTPI-2) (Yang et al, 2015) design will be utilized. The mTPI-2 method uses a Bayesian framework and a hierarchical model to compute the dose escalation based on the interval between the toxicity rate of each dose level and target probability (Guo et al, 2017). This study is designed targeting a dose-limiting toxicity (DLT) rate of 25% with an equivalence interval of 20% to 30%.

A cycle of study treatment is defined as 28 days of continuous daily dosing, according to the cohort and dose level. At the starting dose, patients will be administered HMPL-306 at [REDACTED] mg PO, QD, and the dose will escalate successively according to the sequence of [REDACTED] mg QD, [REDACTED] mg QD, [REDACTED] mg QD, [REDACTED] mg QD, [REDACTED] mg QD, [REDACTED] mg QD, and [REDACTED] mg QD.

The overall study schema of part 1 is presented in Figure 1

Figure 1 Study Schema

Subjects who complete the DLT assessment window and are deemed by the investigator to be benefiting from HMPL-306 treatment will be allowed to continue treatment until disease progression, intolerable toxicity, at the investigator's discretion that the subject can no longer

benefit from the study treatment, withdrawal of consent, lost to follow-up, the end of study, or death, whichever comes first.

Safety Follow-up

Subjects who have completed the study treatment will be evaluated for safety 30 days (± 7) days following the EOT visit for study drug-related AEs until resolution and SAEs until resolution regardless of relationship to study treatment.

Efficacy Follow-up

Subjects who discontinue the study drug due to reasons other than disease progression, death, lost to follow-up, or withdrawal of consent will remain on study and will be followed every 12 weeks (± 14 days) from EOT visit for tumor assessment until disease progression, initiation of new anticancer therapy, withdrawal of consent, lost to follow-up, death, or the end of the study, whichever comes first.

2.3. Determination of Sample Size

2.3.1. Dose Escalation Part

The maximum sample size in this phase will be determined jointly by the sponsor and the investigator. The exact sample size of the mTPI-2 design in the dose escalation part cannot be pre-specified because of the dynamic nature of the Bayesian allocation procedure. Subjects not evaluable for DLT may be replaced, and this may result in the number of subjects enrolled being more than expected. It is estimated that approximately 27 to 36 subjects may be enrolled.

3. ANALYSIS SETS

3.1. Definition of Analysis Sets

Data analyses will be based on the analysis sets defined below. Unless otherwise specified, analyses will be conducted on the basis of first dose of study drug that a patient received.

3.1.1. All Subjects Set

All patients who signed the informed consent.

3.1.2. Safety Analysis Set

The safety analysis set includes all enrolled patients who received at least 1 dose of study drug (HMPL-306). This is the primary analysis set for safety and efficacy analyses.

3.1.3. DLT-Evaluable Analysis Set

The DLT- evaluable analysis set will be determined based on the medical review.

DLT analysis for the Part 1 dose escalation phase will be performed using the DLT evaluable analysis set.

3.1.4. Response Evaluable Analysis Set

The response evaluable analysis set will include all patients who are in the safety analysis set and have a measurable lesion at the baseline tumor assessment, and either (i) have at least 1 post-dose tumor assessment, or (ii) do not have post-dose tumor assessment but have clinical progression as noted by the investigator, or have died before their first post-dose tumor scan. The response evaluable analysis set will be used for analyses of anti-tumor response.

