5.2 Inclusion Criteria

Subjects may be enrolled in this study only if they satisfy all the following criteria:

1. Subjects must be ≥ 18 years of age.
2. Subjects must have an Eastern Cooperative Oncology Group (ECOG) performance status (PS) score of 0 or 1.
3. Subjects must have a measurable or evaluable disease for Part 1 (Dose Escalation) and subjects must have a measurable disease according to Response Evaluation Criteria in Solid Tumors (RECIST) Version 1.1 (or Response Assessment in Neuro-Oncology [RANO] criteria for gliomas) for Part 2 (Dose Expansion).
4. Subjects must have an absolute neutrophil count (ANC) of $\geq 1.5 \times 10^9/L$, platelet count of $\geq 75 \times 10^9/L$, and hemoglobin of ≥ 8 g/dL.
5. Subjects must have adequate hepatic function as evidenced by the following: aspartate aminotransferase (AST) and alanine aminotransferase (ALT) $\leq 3 \times$ upper limit of normal (ULN), except for subjects with liver metastasis who are included if $\leq 5 \times$ ULN and total bilirubin $\leq 1.5 \times$ ULN.
6. Subjects must have serum albumin ≥ 2.8 g/dL.
7. Subjects must have creatinine clearance ≥ 60 mL/min as estimated by the Cockcroft-Gault formula.

8. Subjects must have an international normalized ratio (INR) of ≤ 1.5 or an activated partial thromboplastin time (aPTT) of $\leq 1.5 \times$ ULN.
9. Subjects must be recovered to \leq Grade 1 from all toxic effects of any prior surgery, radiotherapy, or other therapy.
10. Subjects must have recovered from surgery, at least 2 weeks post-surgery prior to starting study drug.
11. For gliomas (Part 1, and Cohort C), subjects must not show enhancing disease on T1-gadolinium-magnetic resonance imaging (Gd MRI).
12. Female subjects of childbearing potential must have a negative serum pregnancy test within 7 days of study drug administration. NOTE: Postmenopausal is defined as ≥ 24 months of amenorrhea and at least 50 years of age.

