9.1.3 Analysis Sets

The following analysis sets are defined for the study:

- Safety analysis set: All enrolled subjects who received at least 1 dose of study treatment will be included in the safety analysis population. Safety evaluation will be performed based on the first dose of study treatment received by a subject. This is the primary population for the safety and efficacy analysis endpoint PFS.

- DLT evaluable analysis set: All subjects enrolled in the dose escalation phase of the study who are evaluable for DLT assessment. A subject is DLT evaluable if he/she meets the following criteria:
 - has received at least 75% of the assigned dose of study medication during the DLT assessment window
- OR
- has not completed the DLT assessment period due to a DLT
- Response evaluable analysis set: All subjects who received study treatment and have a baseline tumor assessment and at least 1 postbaseline assessment will be considered evaluable for antitumor efficacy endpoints such as objective response rate (ORR), disease control rate (DCR), time to response (TTR), and duration of response (DoR)
- PK analysis set: All subjects with at least 1 quantifiable plasma concentration of HMPL-306 will be included in the PK analysis population
- PD analysis set: All subjects with at least 1 quantifiable level of 2-HG in the plasma will be included in the PD analysis population

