5.2.9. Efficacy Analyses

The safety analysis set will be used for PFS, and the response evaluable analysis set will be used for anti-tumor responses such as BOR, DoR, DCR, and TTR. No formal hypothesis testing is planned for this study. Two-sided 95% confidence intervals (CIs) will be calculated in the applicable summary, unless otherwise specified.

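### The SAP calls the safety set primary for efficacy but analyses response on a response-evaluable set, names no set for ORR, and lets some treated, unscanned patients leave the denominator

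*SAP*

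**What the plan says.** **Role of the safety set.** SAP 3.1.2 defines it as all enrolled patients with at least one dose and adds: "This is the primary analysis set for safety and efficacy analyses". Protocol 9.1.3 (Amendment 2) is narrower: "This is the primary population for the safety and efficacy analysis endpoint PFS".

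**Role of the response-evaluable set.** SAP 3.1.4 states: "The response evaluable analysis set will be used for analyses of anti-tumor response". SAP 5.2.9 gives PFS to the safety set and continues: "the response evaluable analysis set will be used for anti-tumor responses such as BOR, DoR, DCR, and TTR". That list omits ORR. In SAP 5.2.9.1 the BOR sentence names the response-evaluable set, the ORR sentence names no set, and DCR is to follow ORR.

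**Who is in it.** Under SAP 3.1.4, patients in the safety set must "have a measurable lesion at the baseline tumor assessment, and either (i) have at least 1 post-dose tumor assessment". The alternative limb (ii) admits those who "do not have post-dose tumor assessment but have clinical progression as noted by the investigator, or have died before their first post-dose tumor scan". Protocol 9.1.3 instead takes treated patients who "have a baseline tumor assessment and at least 1 postbaseline assessment will be considered evaluable for antitumor efficacy endpoints". It sets no measurable-lesion condition and makes no provision for unscanned failures.

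**Who may enter Part 1.** Protocol 5.2, criterion 3, begins: "Subjects must have a measurable or evaluable disease for Part 1 (Dose Escalation". A patient without a measurable lesion is therefore eligible.

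**The concern.** A response rate is only as clear as its denominator. Here the general sentence in SAP 3.1.2 and the endpoint-specific sentences in 3.1.4 and 5.2.9 point to different sets, and ORR is assigned only by inference.

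The response-evaluable set also depends on what happens after the first dose. A treated patient who leaves with no scan, no noted clinical progression and no early death is removed, not counted as a failure. This is foreseeable in dose escalation: the first on-treatment tumour assessment is at 8 weeks (Protocol 6.1.13). Efficacy is shown by dose level and disease type (SAP 5.1.1), so one patient can shift a reported rate a good deal.

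**Working it through.** The plan states no ORR or DCR figure that depends on the denominator, so there is nothing to reproduce. The check is who falls in which set, and then what removal does to a rate.

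**Step 1. Membership by type of treated patient**

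| Treated patient | Safety set | SAP 3.1.4 set | Protocol 9.1.3 set (Amendment 2) |
|---|---|---|---|
| (a) Measurable lesion, no scan, clinical progression or early death | in | in, by limb (ii) | out |
| (b) No scan, no noted progression, no early death | in | out | out |
| (c) Scanned, evaluable-only disease | in | out | in |

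**Step 2. Direction for group (b).** An unscanned patient cannot be a responder or have documented disease control. Removing k such patients leaves the numerator x unchanged and turns x/n into x/(n − k), which is never smaller than x/n. The effect on ORR and DCR is upward, or nil when k = 0 or x = 0.

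**Step 3. Direction for group (c).** This is not fixed, because removal can change the numerator too. Under Protocol Appendix 8, Table 14, a patient with only non-target lesions can be CR, non-CR/non-PD, PD or NE, and its footnote advises against calling such patients stable. SAP Table 2 has no non-CR/non-PD category.

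**Step 4. Size at a dose level.** Assume one responder and the loss of one group (b) patient. Intervals are exact 95% Clopper-Pearson, the method in SAP 5.2.9.1.

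| Treated at the level | All treated | One patient removed |
|---|---|---|
| 3 | 1/3 = 33.3% (0.8 to 90.6) | 1/2 = 50.0% (1.3 to 98.7) |
| 4 | 1/4 = 25.0% (0.6 to 80.6) | 1/3 = 33.3% (0.8 to 90.6) |
| 6 | 1/6 = 16.7% (0.4 to 64.1) | 1/5 = 20.0% (0.5 to 71.6) |

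**Step 5. Size over Part 1, for scale only.** SAP 2.3.1 expects 27 to 36 patients. Assumed, not in the documents: 3 responders, about half with disease control, 0 to 3 patients in group (b), none in (a) or (c).

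- N = 36, k = 0: ORR 3/36 = 8.3%; DCR 18/36 = 50.0%.
- N = 36, k = 3: ORR 3/33 = 9.1%; DCR 18/33 = 54.5%.
- N = 27, k = 0: ORR 3/27 = 11.1%; DCR 14/27 = 51.9%.
- N = 27, k = 3: ORR 3/24 = 12.5%; DCR 14/24 = 58.3%.

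Three such patients would move pooled ORR by about 1 point and pooled DCR by about 5 to 6 points. The SAP does not plan a single efficacy rate pooled over all of Part 1, so the dose-level figures are closer to what will be reported.

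**The case against.** The best defence is that the endpoint-specific text governs. SAP 3.1.4, 5.2.9 and 5.2.9.1 agree on the response-evaluable set for BOR, and ORR is derived from BOR (SAP 4.2.1.2). SAP 3.1.2 then reads as a loose version of the protocol's PFS-only sentence. This largely stands: the working set can be inferred. It does not remove the contrary sentence or supply the missing assignment for ORR.

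Several stronger readings are tempting, and the documents do not support them.

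- *Three live denominators.* A reader might count the protocol's set as a third. Protocol 9.1 leaves analysis detail to the SAP, so it is not a working rival.
- *All unscanned drop-outs vanish.* Limb (ii) of SAP 3.1.4 keeps clinical progressors and early deaths, the most informative failures. SAP 5.2.1 also tabulates reasons for exclusion from each set.
- *Everyone who stops early for toxicity is lost.* Efficacy follow-up (Protocol 6.1.20, SAP 2.2) continues tumour assessment every 12 weeks, and SAP 3.1.4 asks for a post-dose scan, not an on-treatment one. Many such patients stay in.
- *An undeclared change from the protocol.* SAP Section 7 does not list the difference, but SAP Section 1 says the SAP follows Amendment 3, and the protocol available is Amendment 2. The two may differ: Section 7 mentions a DLT-equivalent summary in the protocol that Amendment 2's analysis section does not contain.
- *A DCR spread of 10 points.* This needs assumed counts that credit evaluable-only patients with disease control, which the RECIST appendix advises against.

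It is also fair to say that requiring measurable disease for a response rate is ordinary practice, and that nothing here is tested.

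**Conclusion.** The point holds in a limited form. The SAP contradicts itself on the primary set for efficacy and leaves ORR without a named set. Its response-evaluable set drops two kinds of treated patient: those who leave unscanned without noted progression or early death, and those with evaluable-only disease. Loss of the first kind can only raise ORR and DCR; the direction for the second is open.

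The size cannot be fixed, because the documents give no counts of such patients. It is nil if none occur. At a dose level of 3, one lost non-responder moves 1/3 to 1/2, though both intervals are so wide that neither figure carries much weight alone. Whether the definition departs from the governing protocol cannot be judged without Amendment 3. ORR and DCR are secondary and descriptive, so this is a correction worth making before database lock and not a threat to the trial's primary aim.

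**What to change.** 1. In SAP 3.1.2, limit the safety set's primary role to safety and PFS.
2. In SAP 5.2.9, add ORR by name and state its set; repeat the set in the ORR sentence of 5.2.9.1.
3. Report ORR and DCR on all treated patients beside the response-evaluable result, with unscanned patients scored NE and counted as non-responders.
4. Check the response-evaluable definition against protocol Amendment 3. If it differs, list the change in SAP Section 7.

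The cost is a few sentences, one extra column in the response tables, and slightly lower rates in that column. Making the all-treated result primary would be debatable: RECIST patients without measurable disease cannot reach a PR, so they would lower ORR mechanically. Showing both results avoids that choice and lets the reader see how much the exclusions matter.

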3.2. Protocol Deviation

All major and minor protocol deviations will be reviewed prior to final database lock. Only major protocol deviation will be summarized and all protocol deviations will be listed.

4. ENDPOINTS

4.1. General Principles for Derived and Transformed Data

4.1.1. Reference Start Date and End Date and Study Day

Reference start date is defined as the first date when a non-zero dose of study drug was administrated (first administration/dose date). Day 1 is the day of the first dose of study treatment in Cycle 1.

Study day will be calculated from the reference start date, and it will be used to show start/stop day of assessments and events relative to the first administration of study treatment.

- If the date of the event is on or after the reference start date, Study day = (date of event – reference start date) + 1.
- If the date of the event is prior to the reference start date, Study day = (date of event – reference start date).

In the situation where the event date is partial or missing, the date will appear partial or missing in the listings.

Reference end date is defined as the last date when a non-zero dose of study drug was administered.

4.1.2. Baseline and Change from Baseline

Baseline is defined as the last non-missing assessment prior to or on the first administration of study drug, including scheduled and unscheduled visits, unless otherwise specified. For quantitative measurements,

- change from baseline (CFB) will be calculated as: $CFB = \text{assessment value at visit X} - \text{baseline value}$;
- percentage CFB (% CFB) will be calculated as $\% CFB = (\text{assessment value at each visit X} - \text{baseline value}) / \text{baseline value} \times 100$.

4.1.3. Treatment Period

Unless otherwise specified, the treatment period is defined as the period prior to or on the date of first administration of study drug to 30+7 days (7-day window only replies to parameters collected by visit) after the date of last administration of study drug or prior to the start of a subsequent anti-tumor therapy (whichever comes first). For safety data, only the assessments/events collected during the treatment period will be summarized.

The worst post baseline is defined as the worst assessments/events during the treatment period including both scheduled and non-scheduled visit.

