- ^{7.} Ophthalmologic assessments, including eye appearance, slit lamp examination, best corrected visual acuity, visual field, eye movement, pupil reflex, optical coherence tomography (OCT), and intraocular pressure will be performed during the Screening Period. If the subject has undergone the relevant examinations 60 days before the start of study treatment (C1D1), they need not be repeated. After the start of study drug administration, OCT will be performed at 6 weeks (± 1 week), then OCT, eye appearance, and slit lamp examinations will be performed every 12 weeks (± 1 week) from C4D1 and at the EOT visit. Other ophthalmic examinations are to be performed when clinically indicated. If the subject develops an ophthalmic AE related to HMPL-306, the frequency of the examination should be increased to once every cycle until the adverse event is relieved or stable.
- ^{8.} Hematology includes red blood cell count, hemoglobin, hematocrit, white blood cell count with differential and classifications (absolute neutrophil count, neutrophils % absolute lymphocyte count, lymphocytes %, absolute eosinophil count, eosinophils %, absolute monocyte count, monocytes %, absolute basophil count and basophils %), and platelet count. If abnormal or primitive immature cells are seen, they are also required to be recorded. Any additional routine blood tests during the study shall be arranged by the investigator as needed.
- ^{9.} These tests should be completed within 7 days before the start of treatment; if completed more than 7 days before the first dose, they must be repeated on C1D1 prior to dosing.
- ^{10.} Blood chemistry includes blood urea nitrogen, creatinine, sodium, potassium, magnesium, chloride, calcium, phosphorus, blood glucose, creatine phosphokinase, total bilirubin, direct bilirubin, indirect bilirubin, ALT, AST, ALP, LDH, total protein, and albumin.
- ^{11.} Fasting lipid panel includes total cholesterol, high-density lipoprotein, low-density lipoprotein, and triglycerides.
- ^{12.} Coagulation indicators include PT, aPTT, and INR.

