The following categories of abnormal hepatic laboratory values will be evaluated for any occurrence among all assessments in treatment period.

- Aspartate aminotransferase (AST) > 3,5,8,10, and 20x ULN
- Alanine aminotransferase (ALT) > 3,5,8,10, and 20x ULN
- AST and/or ALT > 3,5,8,10, and 20x ULN
- Total bilirubin elevations > 1.5x, >=2x ULN
- ALP > 1.5x, 2 x ULN
- AST and/or ALT > 3x ULN and (total bilirubin > 1.5x, >=2x ULN) [defined as at least one total bilirubin > 1.5x, >= 2x ULN within 14 days after ALT or AST > 3x ULN]
- Hy's Law criteria: AST and/or ALT > 3x ULN and total bilirubin ≥ 2x ULN and ALP < 2x ULN [defined as at least one total bilirubin >= 2x ULN and all ALP < 2x ULN within 14 days after ALT or AST > 3x ULN]

Additionally, the minimum, and maximum values for each patient over the entire treatment period for each quantitative laboratory parameter will also be derived. The change from baseline will also be calculated using these minimum and maximum values.

All laboratory results in SI units are presented in data listings.

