4.4.3. ECG

Electrocardiogram (ECG) parameters include heart rate, RR interval, PR interval, QT interval, QRS interval, QTcF intervals. Change from baseline to each post-baseline visit will be calculated. For a summary of ECG parameters, both the single 12-lead ECG data and the ECG triplicate assessments on Day 1 of Cycle 1 and Cycle 2 will be included. For the ECG triplicate assessments at a timepoint, the average of the triplicate assessment will be derived to represent the assessment at the timepoint. An overall ECG interpretation include the following categories: Abnormal, clinically significant; Abnormal, not clinically significant ; Normal; and Unknown.

Potentially clinically significant ECG findings will be identified using the criteria which are included in [Table 9](#).

Additionally, the minimum, and maximum values for each patient over the entire treatment period for each ECG parameter will also be derived. The change from baseline will also be calculated using these minimum and maximum values.

Table 9 Potentially Clinically Significant Criteria for ECG

ECG Parameter (unit)	Criterion value
Heart Rate (bpm)	>120

ECG Parameter (unit)	Criterion value
	<50
PR Interval (ms)	≥ 210
RR Interval (ms)	> 1200
	< 500
QRS Interval (ms)	≥ 120
	≤ 50
QT Interval (ms)	≥ 500
	≤ 300
QTcF (ms)	> 450
	> 480
	> 500
	≤ 300
	Increase from baseline > 30
	Increase from baseline > 60
	> 450 and increase from baseline > 30
	> 450 and increase from baseline > 60
	> 480 and increase from baseline > 30
	> 480 and increase from baseline > 60
	> 500 and increase from baseline > 30
	> 500 and increase from baseline > 60

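### SAP definitions of the treatment period conflict, and all of them admit pre-dose Day 1 records to on-treatment safety summaries; the ECG baseline is also ambiguous

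*SAP*

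**What the plan says.** **Treatment period.** SAP 4.1.3, which applies unless something else is specified, says that "the treatment period is defined as the period prior to or on the date of first administration of study drug to 30+7 days" after the last dose, or to the start of a subsequent anti-tumor therapy if earlier. It adds: "For safety data, only the assessments/events collected during the treatment period will be summarized", and "The worst post baseline is defined as the worst assessments/events during the treatment period", with unscheduled visits included. SAP 4.4 and 5.2.11 restate the period for safety data and open it on the date of first administration.

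**Outputs that use it.** The hepatic categories in SAP 4.4.2 "will be evaluated for any occurrence among all assessments in treatment period". Minimum and maximum laboratory, ECG and vital-sign values are taken over the whole treatment period (SAP 4.4.2 to 4.4.4). The potentially clinically significant flags use the same window (SAP 5.2.11.5 and 5.2.11.6), and shift tables run from baseline to the worst post-baseline value (SAP 5.2.11.4 and 5.2.11.5).

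**Baseline.** SAP 4.1.2: "Baseline is defined as the last non-missing assessment prior to or on the first administration of study drug, including scheduled and unscheduled visits". SAP 4.4.3 gives no separate ECG baseline. It says that "the ECG triplicate assessments on Day 1 of Cycle 1 and Cycle 2 will be included", with triplicates averaged at each time point.

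**Day 1 schedule.** Protocol Table 1 schedules vital signs on C1D1. Its footnote 2 puts dosing-day assessments before drug, but exempts ECGs and a few others. Under footnote 9, screening laboratory tests more than 7 days old are not enough: "they must be repeated on C1D1 prior to dosing". Protocol Appendix 1 places C1D1 triplicate ECGs pre-dose and at 1, 2 and 4 hours.

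**The concern.** A toxicity window should contain only exposed time, and a baseline only unexposed time. Neither is secured here. The opening edge of the window lets in values recorded before any drug was taken, so a pre-existing abnormality can appear as an on-treatment one. The baseline wording may let in values recorded after the first dose, so a drug effect can be subtracted from itself. The two errors run in opposite directions.

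ECGs and laboratory abnormalities belong to the primary safety endpoint (SAP Table 1). QTcF prolongation and abnormal hepatic function are named risks in Protocol Table 3, and abnormal hepatic function is the only adverse event of special interest in the SAP.

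**Working it through.** No stated sample size or probability depends on these definitions, so there is no figure of the plan to reproduce. The check compares the definitions, then the entry limits with the flags.

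**Step 1. Which records each definition admits**

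| Record | SAP 4.1.3 | SAP 4.4 and 5.2.11 |
|---|---|---|
| Screening record, earlier date | inside | outside |
| C1D1 vital signs, before dosing | inside | inside |
| C1D1 pre-dose ECG triplicate | inside | inside |
| C1D1 laboratory tests, only if repeated under footnote 9 | inside | inside |
| C1D1 ECGs at 1, 2 and 4 h | inside | inside |

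The first row is the contradiction. The next three remain under every definition because the boundary is a date, not a time.

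**Step 2. Entry limits against flags**

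- QTcF: exclusion criterion 10 begins at 470 ms; SAP Table 9 flags values above 450 ms. Values above 450 and below 470 ms are eligible and flagged. The >480 and >500 ms flags do not overlap with entry.
- AST/ALT: inclusion criterion 5 allows up to 3×ULN, "except for subjects with liver metastasis who are included if" no higher than 5×ULN. The first SAP category is >3×ULN. The overlap is above 3 and up to 5×ULN, with liver metastasis only.
- Total bilirubin: entry up to 1.5×ULN, flag above 1.5×ULN. No overlap.
- Blood pressure: SAP Table 10 flags systolic ≥160 or diastolic ≥105 mmHg. Protocol 5.2 and 5.3 set no blood-pressure limit, so a pre-dose value can qualify.

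Example (assumed values): ALT is 4×ULN on a repeated C1D1 pre-dose sample and 2×ULN on drug. The patient is counted as >3×ULN on treatment although every on-drug value is below it. If that record also serves as worst post-baseline, the shift table shows no improvement. The same record could start the 14-day bilirubin look-ahead in the Hy's Law criterion.

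**Step 3. ECG baseline under two readings of SAP 4.1.2**

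- Read as the dosing event: baseline is the C1D1 pre-dose triplicate.
- Read by date: baseline is the last C1D1 triplicate, at 4 hours post-dose.

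Example (assumed values): QTcF is 430 ms pre-dose, 442 ms at 4 h, and 465 ms at C2D1. The change is 465 − 430 = 35 ms on the first reading and 465 − 442 = 23 ms on the second. The >30 ms category is lost; the absolute >450 ms flag is still met.

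Over a range, let D be the true later rise over pre-dose, a the rise already present at 4 h, and SD the standard deviation of one time-point average. The observed change is taken as Normal with mean D − a and variance 2·SD², so P(flag >30 ms) = 1 − Φ[(30 − (D − a)) / (SD√2)]. With D = 40 ms and SD 6 to 10 ms, all assumed:

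| a (ms) | SD 6 | SD 10 |
|---|---|---|
| 0 | 0.88 | 0.76 |
| 10 | 0.50 | 0.50 |
| 20 | 0.12 | 0.24 |

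**Step 4. Weight of one patient**

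SAP 2.3.1 expects 27 to 36 patients; Protocol Table 5 has eight dose levels.

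- Per level: 27/8 = 3.4 and 36/8 = 4.5. One patient is 1/3.4 = about 30 points or 1/4.5 = about 22 points; in a three-patient cohort, 1/3 = 33 points.
- Total: 1/27 = 3.7 and 1/36 = 2.8, so about 3 to 4 points.

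**The case against.** The strongest reply is that SAP 4.1.3 yields to any other specification, and the two sections that govern safety both specify the date of first dose. That stands for screening records. A reader might infer that entry abnormalities in general will be counted as on-treatment toxicity; the documents do not support this, because on the more specific rule records from before the first-dose date are out.

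Second, a baseline record is by name not post-baseline. This is a fair plain reading for the shift tables, but SAP 4.1.3 defines the term by the treatment period alone. The min/max values, any-occurrence categories and flags carry no such qualifier.

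Third, laboratory exposure is narrow. Protocol Table 1 schedules no C1D1 hematology or chemistry, so only footnote 9 repeats matter, and a C1D1 laboratory or vital-sign baseline is already pre-dose under footnote 2. This stands. It leaves scheduled vital signs and ECGs inside the window, and makes the baseline question essentially one about ECGs.

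Fourth, SAP 4.1.2 refers to the administration, not its date, whereas SAP 4.1.3 does say date. A reader might infer that the SAP fixes the 4-hour ECG as baseline; it does not. But SAP 4.1.1 treats first administration and first-dose date as interchangeable, no text requires a pre-dose value, and ECGs are exempt from the before-dosing rule. The wording is open, not wrong by rule.

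Fifth, the consequences are bounded. TEAEs have their own onset-or-worsening rule (SAP 4.4.1), DLTs their own window and committee review, no hypothesis test is planned, and all laboratory and ECG data are listed by patient. This stands; the harm is to summary tables, not to dose decisions.

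**Conclusion.** The SAP contradicts itself on when the treatment period opens. On every version, pre-dose C1D1 vital signs and ECGs, and laboratory tests if repeated that day, fall inside it and can be tabulated as on-treatment findings. The ECG baseline is an unresolved ambiguity; if resolved by date, later QTcF increases would be understated.

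The frequency of either error cannot be computed from the documents, which give no distribution of entry values or of first-dose QTcF effect. The per-patient weights assume even spread over eight levels; Protocol 4.1.1 allows a cohort to extend to 12, where one patient is 1/12 = about 8 points. The ECG hours come from the supplied protocol, Amendment 2, whereas the SAP cites Amendment 3; SAP 4.4.3 confirms the C1D1 triplicates but not their hours.

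A correction is warranted because the misstated windows feed summaries of the primary safety endpoint in very small groups.

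**What to change.** - SAP 4.1.3, 4.4 and 5.2.11: use one definition, with the treatment period starting at the date and time of first dose.
- SAP 4.1.3 and 4.4.2 to 4.4.4: restrict worst, minimum/maximum, any-occurrence and flag derivations to records after first dose, and exclude the baseline record.
- SAP 4.1.2: define baseline as the last non-missing assessment before the time of first dose. For ECG, use the mean of the C1D1 pre-dose triplicate, or the last pre-dose value if that is missing. Treat the C1D1 1, 2 and 4 h ECGs as post-baseline.

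The cost is SAP wording and a date/time comparison in programming. Protocol 7.1 already has the actual dosing time recorded in the subject diary, and Appendix 1 labels the ECG time points. No new data are needed.
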